The population for the study will be patients with anterior circulation acute ischemic stroke due to blockage of the intracranial internal carotid artery or middle cerebral artery (M1) within 8 hours of onset of symptoms. Typically, IAT is only offered to patients up to 6 hours, with no treatment options directly targeting the clot available after that time. Occlusion of one of these vessels will be determined based on CT angiography, magnetic resonance angiography, or DCA. Only patients 18 or over will be considered for the study. Other inclusion criteria include a score of 8 or greater on the National Institute of Health Stroke Scale (NIHSS, see appendix). Exclusion criteria will include contra-indication for IAT found on initial CT, intracranial hemorrhage, stroke mimics (tumor, herpetic encephalitis, etc.), more than 1/3 hypodensity on non-enhanced head CT prior to intervention, ASPECT Score < 6, and pre-existing disability defined as mRS ≥ 2. Pregnant women will also be excluded.

[figure not shown]

Figure 1: Study design for Phase I

Version: 6.0 5

[figure not shown]

Figure 2: Study design for Phase II

C. Assessment of Resources

The multicenter study will be carried out at up to 6 stroke centers. Each center is expected to have approximately 1 patient per month eligible for the study. Enrollment of patients will be performed at the end of imaging at each institution. At Akron General Medical Center, consent will be obtained within the DCA imaging suite. Consent will be obtained by a person qualified by the local IRB other than the treating physician. At Akron General, consent will be acquired by one of two neurointerventional lab nurses. One of these two nurses is required to be present for treatment of each patient with acute ischemic stroke, regardless of participation in a study. These nurses are familiar with all aspects of the proposed treatment methods and typical outcomes. The nurses will perform documented training on methods for obtaining consent and maintaining confidentiality of data obtained from subjects enrolled in research projects.

D. Study Procedures

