Recruitment will occur within the DCA suite or other imaging suite at each site following imaging to determine if patients meet enrollment criteria. Since eligible patients are typically mentally impaired by the stroke, consent will be provided by a designated caregiver or family member as described in section VIII, unless the patient is found to be competent to give informed consent by the treating stroke team neurologist. For all eligible patients, an 8.5 ml blood sample will be collected followed by the DCA to assess the CIS. Sample specimens will be stored at a temperature of 2°C to 8°C at each institution for a maximum of 28 days

Version: 6.0

before being shipped to Akron General. Akron General will store all samples for long-term at temperatures between -70°C and -80°C until the samples are sent for genetic analysis.

The initial phase of treatment for patients treated with IAT typically takes 2-3 hours in the angio suite to try to remove the clot from the blood vessel. To remove the clot, Trevo stent retriever (Stryker Neurovascular) will be used as the first pass. Patients are then transferred to the neuroscience intensive care unit (routine). The length of stay in the unit varies from patient to patient and will be determined by the local treating team. Patients can be discharged to home care or to a rehabilitation facility depending on their condition, based on the current standard of care. All medications and rehabilitation techniques prescribed for patients following the procedure will be based on the normal standard of care for the treating physician, regardless of the treatment group or classification of the CIS.

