 ADAM17, CNX37 and their related gene pathways.
- Subgroup analysis will be performed for ethnicities.
- Taqman assays and/or exome sequencing of significantly associated SNPs and/or genes.
- Pending results, a future validation study will follow this discovery study by increasing the sample size.

B. Statistical Methodology

Data for the proposed study will be analyzed using comparison of proportions and multivariable logistic regression. Analysis of proportions based on Fisher exact tests will be used to compare rates of good outcomes between the fCIS and pCIS groups as the primary end point for phase I. The influence of successful revascularization on outcomes for patients with fCIS or pCIS will also be analyzed using Fisher exact tests as the secondary end point.

Binary and/or ordinal multiple logistic regression analyses will be used to evaluate the influence of multiple parameters on the likelihood of a good outcome. These parameters will include CIS, mTICI score, NIHSS score, time to revascularization, age, sex, history of diabetes mellitus, history of high blood pressure, history of coronary artery disease. The same analyses will be performed for phase II, instead focusing on the treatment groups rather than the CIS classification.

VI. DATA AND SAFETY MONITORING PLAN

A. Describe any provisions for monitoring the data for safety

A safety committee will monitor the data. The safety committee will be composed of at least 3 voting members. At least two members will be neurologists, neuroradiologists or neurointerventionalists with experience treating acute ischemic stroke who are not investigators at any of the sites. These members will not be affiliated with the institution of the principal investigator, any sub- investigator, or Akron General Medical Center. At least one member with a background in biostatistics who is not an investigator or affiliated with Akron General Medical Center will also be on the committee.

For phase I, the only deviations in normal standards of care are:

Version: 6.0

- 1- the extra few minutes for full DCA for some centers as opposed to injecting only the occluded vessel
- 2- Adding IAT to treatment of patients seen between 6 and 24 hours of onset of symptoms.

The safety committee will be looking at known potential complications for IAT in both fCIS and pCIS groups. These include:

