- A. parenchymal hemorrhage type 2 symptomatic or asymptomatic hemorrhagic transformation within the vascular territory of the index ischemic stroke within 24 hours of treatment
- B. Any neurological worsening (NIHSS increase of 4 points or more) within 24 hours of treatment.

The rate of complications will be assessed by the safety committee after evaluation of 20, 30 and 40 patients. The trial will be stopped for safety if the rate of brain edema and intracranial hemorrhage is significantly larger for the pCIS group than the fCIS group.

The safety committee will meet at the end of phase I and give its recommendation to launch phase two or not depending on their review. The primary reason not to launch phase II would be higher than expected good outcomes for the pCIS patients treated with EVT plus standard of care, giving the indication that IAT should not be withheld from patients during phase II. During phase II, the safety committee will review the data on complications as noted above and percentage of good outcomes after 10 and 20 subjects are evaluated for comparisons between the two treatment groups.

VII. STUDY LIMITATIONS

A. Potential Limitations of Procedures

The primary limitation for phase II is the small sample size. Due to the expected relatively low rates of good outcomes for pCIS patients regardless of type of treatment, the power will not be sufficient to establish whether or not treatment with IAT is beneficial for patients with pCIS. The study will, however, provide the preliminary data needed to plan for a future, larger prospective clinical trial. Potential limitations for the genetic component of this study include DNA damage due to improper handling or storage of blood samples. The Paxgene DNA tubes are designed to stabilize DNA in the blood. However, the tubes will only function properly if the instructions for inverting the tube multiple times and prompt shipment for storage at Akron General are followed.

VIII. ETHICAL CONSIDERATIONS

A. Informed Consent

Enrollment of patients will be performed in an imaging suite at each institution. Once eligibility is determined by the treating physician based on imaging, the consent process will be initiated by a study research coordinator or study nurse. These investigators are familiar with all aspects of the proposed treatment methods and typical outcomes and maintaining confidentiality of data obtained from subjects enrolled in research projects.

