B. Risks and Side Effects

Acute anterior circulation large vessel occlusion ischemic stroke is a serious and potentially fatal condition. Severe disability and death can result regardless of the type of treatment performed. For the proposed study, risk is minimized by treating all patients in phase I with the combination of IAT and standard of care. Randomization of treatment between IAT plus standard of care or standard of care alone is only used for the patients with pCIS in phase II, after establishing a poor rate of good outcomes (< 15%) for those patients with pCIS treated with the combination of IAT and IVT. Patients not enrolled in the study will be treated with the normal standard of care for the participating institution. At Akron General Medical Center the normal standard of care is supportive treatment. The investigators believe there is a risk to treating patients with pCIS with IAT. Opening

Version: 6.0

up the blood supply to ischemic tissue could potentially increase the risk of vasogenic edema and/or hemorrhagic transformation, as well as possible herniation.

It is theoretically possible that results from the genetic analysis could be used to obtain information that could lead to patient discrimination by possible employers and insurance providers. However, given the de-identification at the contributing institution followed by off-site genetic analysis on the de-identified samples, coupled with the genetic data for any individual not being returned to the contributing site, the risk is felt to be negligible.

No compensation to patients for poor outcomes is available for participating in this study. Akron General Medical Center will continue to provide standard care to all enrolled subjects following the initial stroke care, and submit charges for all usual care to the patient's insurance. The patient will be responsible for any charges not covered by insurance. In case of emergency following treatment, patients should follow standard practices to seek urgent medical treatment. Adverse events should also be reported to the principal investigator ([name]) at [contact].

C. Adverse events

Adverse events may include:

- 1. New clot formation due to placement of guiding catheter
- 2. Intra-cranial hemorrhage due to perforation of the treated vessel
- 3. Symptomatic intra-parenchymal hemorrhage
- 4. Extension of clot to a previously patent vessel

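### The protocol does not fix the order of eligibility, consent and the CIS angiogram, so Phase I entry can depend on the CIS and study-only injections can precede consent

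*Combined protocol and SAP*

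**What the plan says.** Some sections put enrollment and consent after imaging:

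- Section III.C: "Enrollment of patients will be performed at the end of imaging at each institution". It does not say which imaging. At the lead site "consent will be obtained within the DCA imaging suite".
- Section VIII.A: "Once eligibility is determined by the treating physician based on imaging, the consent process will be initiated by a study research coordinator or study nurse".
- Section III.B accepts CT angiography, MR angiography or DCA as proof of the occlusion.
- Section I, item C: the CIS is read from the DCA immediately before treatment.

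Others put the CIS angiogram after eligibility:

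- Section III.A has all eligible patients undergo the full DCA with injection of every potential collateral.
- Section III.D: "For all eligible patients, an 8.5 ml blood sample will be collected followed by the DCA to assess the CIS".

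Four further statements bear on the point:

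- Section III.C keeps consent away from the operator: "Consent will be obtained by a person qualified by the local IRB other than the treating physician".
- Section VI.A lists, as a departure from usual care in Phase I, "the extra few minutes for full DCA for some centers as opposed to injecting only the occluded vessel".
- Section VIII.B: "The investigators believe there is a risk to treating patients with pCIS with IAT". It also says that patients who are not enrolled receive the institution's usual care, which at the lead site is supportive treatment.
- Section III.A allows the groups to be balanced if one of them reaches 70%.

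**The concern.** Phase I compares two non-randomized groups defined by the CIS. Such a comparison is interpretable only if entry is settled without regard to the CIS, or at least without regard to CIS and expected outcome together. If a site treats the end of imaging as the end of the full DCA, the physician who decides eligibility has already seen the exposure. The protocol also gives that physician a reason to hold back a pCIS patient (the stated belief that IAT carries a risk in pCIS) and a route for doing so (usual care outside the study).

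Two results are at stake. One is the primary fCIS-pCIS contrast. The other is the pCIS good-outcome rate, which section VIII.B expects to be below 15% before Phase II randomizes. Separately, where the full DCA is not usual practice, the extra collateral injections are made because of the study, and the text does not ensure that they follow consent.

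The visible text does not ask for consecutive enrollment or a log of eligible patients who were not enrolled. Selection could therefore not be detected afterwards.

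**Working it through.** **The plan's own figure.** Section V.A assumes 60% fCIS, 50% good revascularization, and good-outcome rates of 70% and 20% (fCIS with good and poor revascularization) and 20% and 10% (pCIS likewise). Compare fCIS with good revascularization (0.6 × 0.5 = 30% of patients, 70% good outcomes) with all others (70% of patients, (0.3 × 0.20 + 0.2 × 0.20 + 0.2 × 0.10)/0.7 = 17.1%). With alpha 0.025 taken as two-sided, power 0.90 and a continuity correction, the smaller group needs 16 patients and the total is 54. The stated size reproduces, and the order of consent does not enter it.

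**Planned pCIS group.** 60 × 0.4 = 24 patients. The rate is 0.5 × 20% + 0.5 × 10% = 15%, or 3.6 good outcomes. The fCIS rate is 0.5 × 70% + 0.5 × 20% = 45%. The planned rate sits exactly on the 15% boundary: 3/24 = 12.5% and 4/24 = 16.7%, so a single patient changes the reading.

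Everything below assumes an amount of non-enrollment. The documents give none.

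**Entry depends on CIS alone.** Rates within groups are unchanged, but the mix moves. With 60 completers, a share s of pCIS patients not entered gives an fCIS share of 0.6/(0.6 + 0.4(1 − s)). Power is for Fisher's exact test, 45% vs 15%, two-sided 0.05.

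| s | fCIS / pCIS | Power |
|---|---|---|
| 0 | 36 / 24 | 0.65 |
| 25% | 40 / 20 | 0.61 |
| 50% | 45 / 15 | 0.53 |
| 75% | 51 / 9 | 0.31 |

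**Entry depends on CIS and prognosis: effect on the pCIS rate.**

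- Two who would do well are missed: (3.6 − 2)/(24 − 2) = 1.6/22 = 7%.
- Four who would do poorly are missed: 3.6/(24 − 4) = 3.6/20 = 18%.
- Half of those who would do well are missed: 0.075/(0.075 + 0.85) = 8.1%.
- Half of those who would do poorly are missed: 0.15/(0.15 + 0.425) = 26.1%.

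**Entry depends on CIS and prognosis: effect on the contrast.** Suppose CIS has no effect and both groups have the plan's overall rate, 0.6 × 45% + 0.4 × 15% = 33%.

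| pCIS patients not entered | Observed pCIS rate | False-positive probability |
|---|---|---|
| none | 33% | 0.035 |
| 25% of those who would do well | 0.2475/0.9175 = 27% | 0.055 |
| 50% of those who would do well | 0.165/0.835 = 20% | 0.145 |
| 25% of those who would do poorly | 0.33/0.8325 = 40% | 0.060 |
| 50% of those who would do poorly | 0.33/0.665 = 50% | 0.197 |

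The bias can go either way, depending on which patients are held back.

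**The case against.** The sections can be read as consistent. On that reading, the imaging in III.C is the imaging that establishes eligibility, and III.A and III.D then send eligible patients to the CIS angiogram. Being in the DCA suite does not show that the collateral injections are finished. Only the lead site is tied to that suite: III.D and VIII.A allow other imaging suites, and VIII.G adds the emergency department. Even when DCA is the qualifying test, section I, item C separates injection of the ischemic territory from the fuller collateral study, so the occlusion can be shown before the CIS is known. The eligibility criteria in III.B contain no CIS item. Section III.A requires consent from every patient, and item C calls complete films the usual practice of many operators. Figures 1 and 2 are not available here and may show the order.

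Much of this stands. A reader might infer that the protocol requires the CIS to be seen before eligibility is decided, or that the operator also takes consent. The documents support neither: the order is permitted rather than mandated, and consent belongs to other staff. Nor do they show that unconsented study injections will occur. They can occur at those centers that would otherwise inject only the occluded vessel.

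The benign reading is nevertheless not secured. No visible text places consent or a recorded eligibility decision before the collateral injections, or keeps the CIS from the person deciding eligibility. The order in III.D is itself uncertain, because III.A times the same blood sample at 48 to 60 hours after admission. The 70% option in III.A, if used to control entry, needs the CIS to be known first.

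**Conclusion.** The point holds as an unresolved conflict over sequence that leaves Phase I open to selection on the exposure. It should be corrected, but it is not evidence that selection will happen.

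Its size depends on an unknown. Selection on CIS alone costs power: from 0.65 to 0.53 if half of pCIS patients are not entered. Selection on CIS and prognosis moves the pCIS rate off 15%, to 7% or 18% with two or four patients missed. That is enough to fall on either side of the rate that VIII.B ties to Phase II. These figures rest on the planning rates in V.A and on assumed non-enrollment.

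A reader might go further and conclude that the contrast must be biased in favor of the CIS, or that no analysis could repair it. Neither follows. The direction depends on who is held back. The regression in V.B, which includes NIHSS, time to revascularization, age, sex and history, may reduce bias that runs through those variables. It cannot be relied on to remove bias from an operator's unrecorded impression of prognosis.

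In Phase II, entry restricted to pCIS is by design, so knowing the CIS before randomization is not a fault there. The open question in that phase is only when consent is taken relative to any study-only injections.

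**What to change.** Reconcile III.A, III.B, III.C, III.D and VIII.A into one Phase I sequence:

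1. Eligibility is determined and recorded on CT angiography, MR angiography or the occluded-vessel injection. This keeps DCA as a qualifying route.
2. Consent is obtained and time-stamped.
3. The collateral injections follow and the CIS is scored.
4. The patient counts as enrolled whatever CIS is found.

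Remove the 70% balancing option, or restrict it to a rule stated in advance that does not let the operator select individual patients.

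Require each site to keep a consecutive log of patients who meet the criteria but are not enrolled, with the reason and any CIS obtained. The log also allows the planned 60% fCIS share to be checked against all eligible patients.

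For Phase II, state at which point consent is taken relative to any study-only injections.

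The cost is revised protocol and consent wording and the upkeep of a screening log. The needed sample size of 54 is unchanged.
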